Overall Study Design: Interventions will address three primary areas to improve vaccination uptake: (1) process (text messages); (2) teachable moment messaging (motivational interviewing); and (3) barrier elicitation and reduction (electronic survey with tailored questions/prompts). In our selection of potential interventions, we will use the Community Preventive Services Task Force (CPSTF)⁹ and the NIH Behavior and Social Sciences Research-Coordinating Committee Rapid Working Group on COVID-19 Vaccine Communication guide, among other resources.¹⁰ We will work with the NIH RADxSM-UP Coordination and Data Collection Center (CDCC) to ensure collection of Common Data Elements.

Table 2. Experimental conditions in the 2³ factorial design for the COVID-19 vaccine intervention

Condition	Factor		
	Process Improvement	Teachable Moment Messaging	Barrier Elicitation and Reduction
1	No	No	No
2	No	No	Yes
3	No	Yes	No
4	No	Yes	Yes
5	Yes	Yes	Yes
6	Yes	Yes	No
7	Yes	No	No
8	Yes	No	Yes

Outcome metrics characterizing SARS-CoV-2 vaccine uptake. Our **primary outcome** will be intention to receive a COVID-19 vaccine post-intervention. We will measure this with the question “How likely are you to get an approved COVID-19 vaccine?” and “If you have received 1 dose of the Janssen vaccine or 2 doses of the Moderna or Pfizer vaccine, how likely are you to get an approved booster shot?” We will compare intention to receive a COVID-19 vaccine or booster among those receiving the interventions compared to those not receiving the intervention (see details on analysis below).

Our **secondary outcome** will be vaccine uptake, including self-report of receiving an initial dose of any approved vaccine, two doses of Pfizer or Moderna vaccines, or a booster of any approved vaccine. We will request the manufacturer of the vaccine and the approximate dates the vaccine was received from the participant.

Aim 2.1. Pilot Implementation.

Study Design. Participants at the pilot sites will be randomized to receive a text message and/or education message (detailed below) delivered through a tablet or no intervention. We will also conduct a pilot of motivational interviewing messages that are tailored based on antibody test results (or lack of testing if the participant declines an antibody test).

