 6. We will send participants a RedCap survey link through text message or email 30 days and 60 days after the intervention to assess intent to be vaccinated for COVID-19 and vaccine uptake, allowing time for both doses of the Pfizer and Moderna, single dose of Jansen's COVID-19 vaccine, or boosters of vaccines to be delivered. We will also send up to three daily reminders to the participant to complete the common data elements survey if they did not complete it after the intervention.
 7. For participants who agree, we will contact up to 60 participants to participate in an evaluation interview to help the personnel determine what did and did not work well during the intervention. This will be a 30 minute to one hour interview.

At all events, key personnel will also conduct a field observation of how the events flow, including external factors such as weather or logistical problems and where challenges to implementing the study or recruiting participants occurred. We will also conduct evaluation focus groups with event site staff to determine what did and did not work during the event.

We expect to recruit 2000 participants over the entire study period (Aim 2.1 and 2.2).

Factorial design. In a factorial research design, two or more independent variables are concurrently examined within the same trial. The three factors are crossed with one another to create a total of eight experimental conditions. An equal number of participants are randomly assigned to each condition, using a random number generator. This is not an 8-arm randomized controlled trial, but instead allows for an efficient examination of main effects for each variable in a sample of 2000 participants (including Aim 2.1 and Aim 2.2).

This approach allows examination of three key treatment development questions in a much more time-efficient and economical manner by simultaneously performing three studies within the single trial. This achieves power to detect between-group differences that is equivalent to performing three separate randomized trials. Investigators who are providing the intervention and conducting analysis will be not be masked to study assignment due to challenges in maintaining the masking in an educational intervention. For all sites, including Aims 2.1 and 2.2, we expect to recruit 2000 participants.

Identifiers might be removed and the de-identified information may be used for future research without additional informed consent from the subject.

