COVID-19 incidence, particularly among underserved minority and rural Oklahomans. Oklahoman's are also reporting SARS-CoV-2 vaccine hesitancy and signs of slowing vaccine uptake, with increased hesitancy among American Indian and rural populations. The project aims to work with ongoing community testing events to implement interventions to improve vaccine uptake among Oklahoma's underserved populations.

I. Statistical Methods

Aim 1 Analysis. Digitally recorded focus groups will be securely uploaded to protected servers and transcribed using NVivo Transcription. Transcriptions will be team coded for conceptual themes using QSR NUDIST Vivo12 Pro for Windows.¹⁶ Investigators will develop a code book. Throughout the coding process, qualitative data will be categorized, connections made between categories, and core categories identified and systematically linked to other categories. Focus group data will inform intervention selection and needed modifications for community acceptability/relevance.

Aim 2 Analysis. All analyses are intent-to-treat. Outcome measures will be assessed at baseline, 30 days, and 60 days follow-up. At the outset, we will examine the frequency distributions of all variables. We will compare the baseline characteristics to assess whether randomization distributed covariates evenly. We will determine whether there is differential dropout and consider developing probability-of-completion weights to obtain unbiased estimates of treatment effect.

The primary analysis will assess the effects of each intervention component in terms of its association with the primary outcome (intent to receive a COVID-19 vaccine immediately after the interventions are completed). Cross-sectional analyses will be conducted for outcomes assessed at 30 and 60 days. For binary outcomes, chi-square tests will be used to compare the outcomes between groups. For continuous outcomes, two-sample t-tests or Wilcoxon rank sum tests, whichever is more appropriate, will be used to compare between groups. A longitudinal analysis using Generalized Estimating Equations (GEE) techniques will also assess the overall impact of the intervention by including data from all follow-up time points.

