As a secondary analysis, we will compare vaccine coverage among counties with an intervention compared to counties without intervention to see whether coverage increased in the study counties using a chi-square test. We will use publicly available data from the Oklahoma State Department of Health and/or Centers for Disease Control and Prevention for this analysis.

Sample size and power calculations. Power calculations are based on our primary analysis, which is to assess the effect of each intervention component on increased intention to receive a COVID-19 vaccine immediately after the intervention. This is a two-sample comparison between participants that receive one intervention component and those that receive the control. Our pilot implementation will include a single site with an estimated 500 participants.

Our outcome of interest is also assessed at 30 and 60 days follow-up to measure intention to receive a COVID-19 vaccine, which allows us to use a longitudinal generalized estimating equations approach wherein power is proportional to the within-site

correlation. Using PASS v16, we assume the intra-cluster correlation within each site is 0.01. Our power analysis is based on data from both pilot and full implementation of the study results. Assuming a minimum n=167 participants per site for a minimum of sites, a Type 1 error rate of 0.05, and an estimated standard deviation of 5, we have over 80% power to detect a mean difference of 20.

Data and Safety Monitoring Plan

Drs. [name] and [name] assure that oral informed consent is obtained prior to conducting the focus groups (Aim 1) and written informed consent and HIPAA authorization are obtained for the intervention (Aim 2) prior to performing any research procedures, that all subjects meet eligibility criteria, and that the study is conducted according to the IRB-approved research plan.

Study data are accessible at all times for the PI/PD to review. [name] will review the study conduct weekly and the PI/PD will review the study conduct on a monthly basis. Study conduct will include accrual, drop-outs, and protocol deviations. The PI/PD will review adverse events individually in real-time and in aggregate on a weekly basis.

COLLECTION AND REPORTING OF SAEs AND AEs

For this study, the following standard AE definitions are used:

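### Vaccine uptake is cumulative and dated, but the plan tests it separately at days 30 and 60 with no rule linking the surveys; this wastes known vaccination status and can bias the day-60 comparison in either direction

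*Combined protocol and SAP*

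**What the plan says.** Section D (outcome metrics) states that the secondary outcome "will be vaccine uptake, including self-report of receiving an initial dose of any approved vaccine", and goes on to include completed two-dose courses and boosters. It adds: "We will request the manufacturer of the vaccine and the approximate dates the vaccine was received from the participant". Step 6 of the Aim 2.2 procedure, like the matching pilot step, fixes the timing: "We will send participants a RedCap survey link through text message or email 30 days and 60 days after the intervention".

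The Aim 2 Analysis in section I says "Cross-sectional analyses will be conducted for outcomes assessed at 30 and 60 days" and then "For binary outcomes, chi-square tests will be used to compare the outcomes between groups". A GEE analysis "will also assess the overall impact of the intervention by including data from all follow-up time points". On missing follow-up the plan says: "We will determine whether there is differential dropout and consider developing probability-of-completion weights to obtain unbiased estimates of treatment effect".

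The power paragraph connects GEE with intention and does not name uptake: "Our outcome of interest is also assessed at 30 and 60 days follow-up to measure intention to receive a COVID-19 vaccine". The documents give no survey response rate, no wording for the uptake item at day 60 (any dose, or doses since the last survey), no analytic use of the dose dates, and no rule for a participant who answers only one of the two surveys.

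**The concern.** A participant who reports a dose at day 30 is vaccinated at day 60 whether or not the second survey is returned. A cross-sectional day-60 test in the usual sense uses day-60 answers, so this person is missing from it. Likewise, a participant who skips day 30 and at day 60 dates a dose to the first 30 days adds nothing to the day-30 test.

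Two things are at stake. One is precision, which is lost even when silence has nothing to do with vaccination. The other is bias. If day-60 response differs between people already vaccinated by day 30 and the rest, a component that brings vaccination forward changes the mix of who answers, and the day-60 difference moves with it. Uptake is secondary, but it is the behaviour that the project sets out to change.

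**Working it through.** **The plan's own figure.** There is none for uptake. The power statement (mean difference 20, SD 5) concerns intention and does not bear on this point.

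**Inputs from the documents.** 2000 participants over Aims 2.1 and 2.2, equal allocation, surveys at days 30 and 60, type 1 error 0.05 (taken as two-sided). If all 2000 are randomised on a factor, there are 1000 per level.

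**Assumed inputs, none of them in the documents.** Day-30 response is 60%. Day-60 response is 20% among day-30 non-responders, and 70% among day-30 responders not vaccinated by day 30. For day-30 responders already vaccinated by day 30 it is rv, which is varied. Uptake with the component is 16% by day 30 and 20% by day 60; without it, 10% and 15%. The true day-60 difference is 5.0 points. Site clustering is ignored.

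**Formulas.** Let A and B be uptake by days 30 and 60. The overall day-60 response is e = 0.6·rv + 0.4·0.2 for early vaccinees and u = 0.6·0.7 + 0.4·0.2 = 0.50 for everyone else.
- Day-60 responder estimate: [A·e + (B−A)·u] / [A·e + (1−A)·u].
- Two-interval estimate: 1 − (1−h1)(1−h2), where h1 = A comes from everyone with known day-30 status and h2 = (B−A)/(1−A) from those unvaccinated at day 30 who answer at day 60. It returns B. Its variance is Greenwood's.

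**Step 1: who contributes.** Day-60 responders: 2000 × 0.50 = 1000. Answering either survey: 2000 × (0.6 + 0.4 × 0.2) = 1360.

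**Step 2: equal response (rv = 70%).** Both estimates are unbiased.
- Cross-sectional SD = √(0.20·0.80/500 + 0.15·0.85/500) = 2.40 points; power = Φ(5/2.40 − 1.96) = 55%.
- Two-interval, component level: 0.80² × [0.16/(680·0.84) + 0.0476/(420·0.9524)] = 0.000255. Control level: 0.85² × [0.10/(680·0.90) + 0.0556/(450·0.9444)] = 0.000213. SD = √0.000468 = 2.16 points; power 64%.
- Simulation (4000 trials) agrees: SD 2.43 against 2.18, power 55% against 64%.

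**Step 3: response depends on vaccination by day 30.** Worked example at rv = 50%, so e = 0.38. Component: (0.16·0.38 + 0.04·0.50)/(0.16·0.38 + 0.84·0.50) = 0.0808/0.4808 = 16.8%. Control: 0.063/0.488 = 12.9%. Difference 3.9 points.

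| rv | Day-60 responders: difference (true 5.0) | Two-interval |
|---|---|---|
| 85% | 5.7 | 5.0 |
| 70% | 5.0 | 5.0 |
| 50% | 3.9 (power 40%) | 5.0 (power 64%) |
| 35% | 3.0 (power about 27%) | 5.0 (power 64%) |

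Now let the component only speed up uptake: 15% against 10% by day 30, and 20% in both by day 60. The responder difference is −1.0 points at rv = 50% (rejects 7%), −1.9 at 35% (12%) and +0.7 at 85%. The two-interval estimate stays at 0.

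**Step 4: where the two-interval analysis fails.** Take the same acceleration-only case, but let people vaccinated on days 31–60 answer at the same reduced rate as early vaccinees. At 50%, h2 is 0.019/0.419 against 0.038/0.438, giving estimated uptake of 18.9% against 17.8%: +1.0 points when the truth is 0. At 35% it is +1.9. Rejection is about 8% and 14%, while the cross-sectional test stays at 0 and 5%. With the true 5-point gain the two-interval estimate remains closer: 5.2 against 4.1 at 50%, and 5.4 against 3.4 at 35%.

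**Step 5: plain carry-forward.** Keeping day-30 positives while dropping silent day-30 negatives, at rv = 70%, gives 0.1288/0.5288 − 0.0930/0.5180 = 6.4 points instead of 5.0. It is biased upwards.

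**Step 6: motivational interviewing.** The pilot (about 500 participants) describes piloting and observing this factor but not randomising it, leaving (2000 − 500)/2 = 750 per level. Both SDs rise by √(1000/750) = 1.155, and the powers in step 2 become 44% and 52%.

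**The case against.** A reader might infer that cross-sectional testing at day 60 necessarily biases an accelerating component downwards. The documents do not support that. They give no response rates; the bias is zero when early vaccinees answer like everyone else and upward when they answer more. The direction is unknown before data are collected.

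A reader might also infer that the plan says known vaccinations will be discarded. It does not. The discarding follows from the ordinary meaning of a cross-sectional analysis combined with silence on linkage. The analyses are declared intent-to-treat, and the dates would allow status to be derived. If the day-60 item asks about any dose since the event, nothing is lost among day-60 responders. This makes the point a missing rule that should be written, not a declared error.

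The planned GEE and completion weights are relevant. GEE uses the day-30 answers but does not fill in a known day-60 status, and the power paragraph ties it to intention. Weights that use day-30 survey status do remove the bias in the step 3 scenarios (4.9 to 5.1 when the truth is 5.0), though with an SD of about 2.9 against 2.2 points. The plan only undertakes to consider weights and names no covariates, so this mitigates the problem without resolving it.

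The strongest objection is step 4: if late vaccinees also answer less, the proposed analysis can credit a component that only brings vaccination forward, while the planned test holds its size. This stands. Neither method is better in every case, which is why the responder comparison should be kept as a sensitivity analysis.

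**Conclusion.** The point holds in a conditional form. The plan collects the dates but does not use them, and on its ordinary reading drops participants whose uptake status is known. Under the assumed rates the precision loss is 55% against 64% power at 1000 per level (44% against 52% at 750), and it needs no differential response. Bias in the day-60 difference arises only if day-60 response depends on vaccination by day 30. Across the response rates tried it ran from about −2 to +0.7 points, against a true difference of 5 or 0.

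All these sizes rest on assumed response and uptake rates. The two-interval analysis itself assumes that day-30 response is unrelated to vaccination and that day-60 response is unrelated to vaccination after day 30. The change is worth making because it uses data already being collected. Uptake is secondary, so the analysis of intention immediately after the intervention is untouched.

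**What to change.** In the Aim 2 Analysis of section I:
- Make the main uptake analysis a two-interval (0–30 and 31–60 days) discrete-time or Kaplan-Meier analysis of first dose after the event date, built from both surveys and the reported dates. Censor unvaccinated participants at their last completed survey.
- Report cumulative uptake by day 30 and by day 60 for each factor level, with differences and 95% confidence intervals.
- State that positives will not simply be carried forward among responders.
- Keep the day-60 responder comparison as a sensitivity analysis, with completion weights whose covariates include day-30 vaccination status.
- State the two response assumptions, and that if late vaccinees answer less the main analysis can favour a component that only accelerates uptake.
- Specify that the uptake item at each survey asks about any dose since the event, with its date.

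The cost is SAP wording, one derived variable and, if needed, a small clarification of the survey item. No extra participants or visits are required.

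### The primary comparison of post-intervention intention is described only as unadjusted two-sample tests, although intention is also asked at baseline; prespecified adjustment would gain precision at almost no cost

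*Combined protocol and SAP*

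**What the plan says.** All places are in the combined protocol and SAP.

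- **Section I, Aim 2 Analysis, primary analysis:** "The primary analysis will assess the effects of each intervention component in terms of its association with the primary outcome", namely intention immediately after the interventions.
- **Same paragraph, test for a yes/no outcome:** "For binary outcomes, chi-square tests will be used to compare the outcomes between groups".
- **Same paragraph, test for an outcome on a numerical scale:** "For continuous outcomes, two-sample t-tests or Wilcoxon rank sum tests, whichever is more appropriate, will be used to compare between groups".
- **Same paragraph, longitudinal model:** a GEE analysis "will also assess the overall impact of the intervention by including data from all follow-up time points". No covariate or baseline term is given for it.
- **Section I, Sample size and power calculations:** the primary analysis is described again: "This is a two-sample comparison between participants that receive one intervention component and those that receive the control".
- **Baseline data:** section I states that "Outcome measures will be assessed at baseline, 30 days, and 60 days follow-up". The one stated use of baseline data in comparing groups is a balance check: "We will compare the baseline characteristics to assess whether randomization distributed covariates evenly".
- **Timing of the question:** in the intervention procedures of Aim 2.1 and Aim 2.2, intention is asked at step 3, the interventions follow at step 4, and intention is asked again in the exit survey at step 5 of the same visit.
- **Scale:** the outcome metrics under Aim 2 give two likelihood questions (vaccine and booster) without response options.

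**The concern.** When the same attitude is asked twice in one visit, the first answer usually predicts much of the second. A comparison of exit answers alone leaves that predictable person-to-person variation in the standard error. The plan collects the baseline answer but gives it no stated role in estimating any effect.

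At stake is the ability to detect small effects. The text message takes under a minute, the tablet message about ten and the interview about five, so small shifts are plausible, though the documents name no such target. Motivational interviewing has the least data: the pilot procedure describes no randomisation of it, so its randomised comparison rests on Aim 2.2 alone.

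**Working it through.** **1. The plan's own power figure.** Section I assumes at least 167 participants per site, SD 5, Type 1 error 0.05, a mean difference of 20, and for clustering, "we assume the intra-cluster correlation within each site is 0.01". It claims over 80% power. The number of sites does not appear in the text, so I take the least favourable case of one site.
- Standardised difference: 20 / 5 = 4 SD.
- Design effect: 1 + (167 − 1) × 0.01 = 2.66.
- Effective size per group: 83.5 / 2.66 = 31.4.
- SE = 5 × √(2 / 31.4) = 1.26, and 20 / 1.26 = 15.8, so power is about 100%.

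The claim is true as a lower bound. A 4 SD target is detected under any analysis, so it cannot show whether extra precision is needed.

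**2. Inputs for the comparison of analyses.**
- Total of 2000 over Aims 2.1 and 2.2; pilot of about 500 (documents).
- Text and education: 1000 per group. Equal allocation is stated for the eight factorial conditions; for the pilot it is my assumption.
- Motivational interviewing: (2000 − 500) / 2 = 750 per group.
- Assumed: two-sided 0.05 (sidedness is not stated), individual randomisation without a design effect, r from 0.3 to 0.7, and an illustrative true difference of 0.10 SD.

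**3. Formulas, in SD units with n per group.**
- Unadjusted: SE = √(2/n).
- Adjusted for baseline: SE = √(2/n) × √(1 − r²).
- Change score: SE = √(2/n) × √(2(1 − r)).
- Power = Φ(difference/SE − 1.96).
- Adjusted to change-score variance: (1 − r²) / [2(1 − r)] = (1 + r)/2.

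**4. Adjusted against unadjusted, true difference 0.10 SD.**

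| r | Variance removed | Power, 1000 per group | Power, 750 per group |
|---|---|---|---|
| unadjusted | none | 61% | 49% |
| 0.3 | 9% | 65% | 53% |
| 0.5 | 25% | 73% | 61% |
| 0.7 | 49% | 88% | 77% |

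Worked line, n = 1000: unadjusted SE = √(2/1000) = 0.0447 and 0.10/0.0447 − 1.96 = 0.28, so power is 61%. At r = 0.5, SE = 0.0447 × √0.75 = 0.0387 and 0.10/0.0387 − 1.96 = 0.62, so power is 73%.

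**5. Adjusted against a change score, 1000 per group, 0.10 SD.** The power section speaks of an increase in intention, which could mean change from baseline.

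| r | Variance ratio (1 + r)/2 | Change score | Adjusted |
|---|---|---|---|
| 0.3 | 0.65 | 47% | 65% |
| 0.5 | 0.75 | 61% | 73% |
| 0.7 | 0.85 | 82% | 88% |

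**6. Larger effects.** At 0.20 SD the unadjusted test already has 99.4% power with 1000 per group and 97.2% with 750. The largest possible gain is therefore 100 − 97.2 = 2.8 points.

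**7. If the item is dichotomised.** Assume a five-level item with shares of 30/20/15/15/20% and the top two levels counted as yes. For five-level items correlating 0.3, 0.5 and 0.7, a risk difference adjusted for the five-level baseline has about 6%, 18% and 37% of its variance removed. If baseline is dichotomised too, the figures are about 5%, 14% and 30%.

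**8. Site.** At an intra-cluster correlation of 0.01, adjusting for site removes about another 1%.

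**The case against.** The strongest reply is that nothing is invalid. Under randomisation the listed tests give valid comparisons. Neither r nor 0.10 SD comes from the documents, and at r = 0.3 the gain at 0.10 SD is only about 4 points. All of that stands, and it limits the point to efficiency.

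A reader might infer that the plan assigns no test at all to the primary outcome, because the list of tests follows a sentence about 30 and 60 days. The documents do not support that. The list is by outcome type, without restriction to the later visits. The power section calls the primary analysis a two-sample comparison and plans on a mean difference with an SD. Read together, these plausibly cover the primary outcome. What stays open is the response scale and the choice between t-test and Wilcoxon.

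A reader might also infer that baseline is certainly ignored. The mention of an increase could mean a change score, and the GEE might include baseline. Neither is specified. If a change score is meant, the gain at r = 0.7 is from 82% to 88%, not from 61% to 88%.

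Finally, because step 3 mentions only a vaccine and the exit survey a vaccine or booster, a reader might infer that the baseline item does not match for people already vaccinated. That is only a possibility: step 3 refers to questions in the plural, and section I says the outcome measures are assessed at baseline.

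**Conclusion.** The point holds as a missed, nearly free gain in precision. As written, the primary comparison is an unadjusted two-sample one, and no listed method states a baseline term although the baseline answer is collected. For a difference in means, adjustment removes 9% to 49% of the variance for assumed r of 0.3 to 0.7. At 0.10 SD this is worth about 4 to 27 power points with 1000 per group (61% to between 65% and 88%) and about 4 to 28 with 750 (49% to between 53% and 77%). It is worth less than 3 points at 0.20 SD or more.

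The figures rest on the assumed r, two-sided 0.05, equal allocation in the pilot and a linear analysis. They do not carry over to a Wilcoxon test, an ordinal model or an odds ratio. The documents do not support reading this as bias, nor as proof that the trial is underpowered. It is an optional efficiency improvement.

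**What to change.** In section I, Aim 2 Analysis:

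- State how the intention item is scored, because that decides the model.
- Make the primary analysis of immediate post-intervention intention a regression adjusted for baseline intention and site: linear for a scored item, with a standardised risk difference if the item is dichotomised.
- Estimate the text and education effects from all Aim 2 participants. Estimate the motivational-interviewing effect from Aim 2.2 participants only, because the pilot procedure describes no randomisation of it.
- Keep the unadjusted two-sample test as a sensitivity analysis.
- Say how a missing baseline answer is handled, since section H allows participants to skip questions and no one should leave the intent-to-treat analysis for that reason.

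Cost: a few sentences and about one degree of freedom per covariate term. For the baseline term at 2000 participants, the variance factor is about 1998/1997 = 1.0005. Baseline intention is already collected and site is known, so no new data and no extra participants are needed.
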